### 9.8.1.2. HYPOTHESIS TESTING

The null hypothesis is that the average change in weekly number of cataplexy attacks from the two weeks of the OL SDP to the two weeks of the DB RWP on JZP-258 ( $\mu_{\text{JZP-258}}$ ) is equal to the average change in weekly number of cataplexy attacks from the two weeks of the OL SDP to the two weeks of the DB RWP on placebo ( $\mu_{\text{Placebo}}$ ). The alternative hypothesis is that  $\mu_{\text{JZP-258}}$  is not equal to  $\mu_{\text{Placebo}}$  i.e.,

$$H_0: \mu_{\text{JZP-258}} - \mu_{\text{Placebo}} = 0$$

$$H_1: \mu_{\text{JZP-258}} - \mu_{\text{Placebo}} \neq 0$$

### 9.8.1.3. MISSING DATA METHODS FOR PRIMARY EFFICACY ENDPOINT

For subjects without post-randomization daily cataplexy attack data, the average weekly number of cataplexy attacks from the OL SDP will be carried forward using a BOCF approach.

### 9.8.1.4. PRIMARY ANALYSIS OF PRIMARY EFFICACY ENDPOINT

The average weekly number of cataplexy attacks over the two weeks of the OL SDP and DB RWP as well as the change in average weekly number of cataplexy attacks from the two weeks of the OL SDP to the two weeks of the DB RWP will be summarized by randomized treatment group and analyzed based on the EFF.

For the primary analysis of the primary efficacy endpoint, an analysis of covariance (ANCOVA) will be performed using the PROC GLM SAS procedure. The model will include the change in average weekly number of cataplexy attacks from the two weeks of the OL SDP to the two weeks of the DB RWP as the

dependent variable; the treatment group and Pre-randomization Group (refer to section 7.3) as fixed effects as well as the average weekly number of cataplexy attacks over the 2 weeks of the OL SDP as covariate. All group comparisons from the ANCOVA model will be based on Type III sum of squares. Least square mean (LS mean) and standard error (SE) will be provided for each treatment group. The difference between these two LS means along with the SE of the difference, 95% confidence interval (CI) and associated p-value corresponding to testing the hypothesis of no difference between the treatment groups will also be provided.

The normality assumption of the ANCOVA model will be examined by residual analysis using the Shapiro-Wilk test at a 0.05 significance level. If the normality assumption is considered violated, a non-parametric ANCOVA with the covariate and response variables replaced by their ranks (Conover and Iman 1982) will be used for the primary efficacy analysis of the primary efficacy endpoint. In the event of ties in the baseline or change from baseline, average ranks will be used. The ranks will be used in the ANCOVA with the rank for the change from baseline as the dependent variable, treatment and Pre-randomization Group as fixed effects, and the rank for the baseline value as the covariate. P-values will be presented from the rank based ANCOVA. Location shift between the change in the average weekly number of cataplexy attacks between the two treatment groups and asymptotic 95% confidence intervals will be presented using the Hodges-Lehman estimator (Hodges and Lehman 1962).

Listings of all reported cataplexy attacks and average weekly cataplexy attacks will be provided.

The following figures will also be provided:

- Spaghetti plot of the average weekly number of cataplexy attacks across the Main Study periods, excluding placebo data, overall and by Pre-randomization group
- Box plot of the change in average weekly number of cataplexy attacks from the two weeks of the OL SDP to the two weeks of the DB RWP by randomized treatment group

#### 9.8.1.5. SENSITIVITY ANALYSIS OF PRIMARY EFFICACY ENDPOINT

- **Sensitivity to analysis population:** The primary efficacy analysis will be repeated based on the PP if that analysis population is different from the EFF.
- **Sensitivity to missing data assumption**

The proposed primary method of handling missing data makes the assumption that a subject's average weekly number of cataplexy attacks during the DB RWP will remain the same as during the OL SDP i.e., that the subject's average weekly number of cataplexy attacks will not increase after discontinuation from study drug. This is a conservative approach as it would tend toward smaller treatment effect. Additionally, to assess robustness of the primary method of averaging the non-missing weekly cataplexy diary values, regardless of the number of non-missing values available over the two-week DB RWP, sensitivity analyses will be performed.

It is noted that this is an enriched study design including subjects responsive and compliant to treatment. In a similar ongoing study with Xyrem discontinuation from study drug occurring during the DB RWP was rare. Hence, the following sensitivity analyses will be performed only if more than 5% of the subjects has missing either week 1 or week 2 cataplexy attack data during the DB RWP in the EFF.

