9.10 Efficacy Analyses

Efficacy analyses will be performed with the Efficacy Population by randomized treatment group.

Efficacy assessments in general will be comparisons of the measurement(s) made during or at the end of the 2 weeks of the Stable-Dose Period compared with the 2 weeks or the end of the Double-Blind Randomized-Withdrawal Period.

A hierarchical group sequential testing strategy, described in Section 9.14 and Section 9.15, will be used to control the family-wise Type I error rate at the 0.05 significance level for two-sided testing across the primary and key secondary endpoints. All other efficacy endpoints will be tested without multiplicity adjustments and nominal p-values provided.

Sensitivity analyses including use of imputation methods, such as multiple imputations for missing data, on the primary and key secondary efficacy endpoints will be used to assess robustness. These analyses and methods will be described in the SAP.

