9.10.1 Primary Efficacy Analysis

For the primary endpoint, the change in the weekly number of cataplexy attacks from the 2 weeks of the Stable-Dose Period to the 2 weeks of the Double-Blind Randomized-Withdrawal Period will be assessed. For subjects with at least one day of cataplexy attack data, the weekly number of cataplexy attacks will be the average number of daily attacks from days with non-missing data within the 2 week period, and then multiplied by 7.

An analysis of covariance (ANCOVA) model will be used to assess the endpoint. The SAS procedure PROC GLM will be used to carry out the analysis. The model will include treatment group and Pre-randomization group as fixed effects. The weekly number of cataplexy attacks during the Stable-Dose Period will be included in the model as a covariate. The estimate for the treatment difference of JZP-258 versus placebo and the 95% CIs will be presented. The normality assumption of the ANCOVA model will be examined by residual analysis using the Shapiro-Wilk test. If the normality assumption is considered violated at the 0.05 significance level, a non-parametric ANCOVA with the data replaced by their ranks will be used.

The number of cataplexy attacks will be summarized by week.

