### **3.6. CHANGES TO ANALYSIS FROM PROTOCOL**

For the purpose of the main efficacy analysis (primary and all secondary endpoints), the Baseline Observation Carried Forward (BOCF) method will be used to impute missing results for subjects without post-randomization data. The PA 5 does not suggest any specific methodology and the study team agreed to apply the BOCF approach.

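### The SAP makes the protocol's missing-data sensitivity analyses conditional on a pooled 5% threshold, does not list this as a change, and calls BOCF conservative without saying for which arm

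*SAP*

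**What the plan says.** Protocol 9.10 states that "Sensitivity analyses including use of imputation methods, such as multiple imputations for missing data, on the primary and key secondary efficacy endpoints will be used" as a check on robustness, and adds: "These analyses and methods will be described in the SAP". It gives no threshold below which they would be skipped.

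SAP 9.8.1.5 describes a control-based multiple imputation (MI) and an LOCF analysis, but says of them that "sensitivity analyses will be performed only if more than 5% of the subjects has missing either week 1 or week 2 cataplexy attack data" in the double-blind period, counted in the efficacy population (EFF). The MI text treats a week as missing when it has no data at all. SAP 9.8.2.4 handles ESS by reference back to this section, without LOCF.

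SAP 3.6 lists one change from the protocol, the use of BOCF: "The PA 5 does not suggest any specific methodology and the study team agreed to apply the BOCF approach". The 5% condition is not there.

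On BOCF, SAP 9.8.1.5 explains the assumption that "the subject's average weekly number of cataplexy attacks will not increase after discontinuation from study drug" and concludes: "This is a conservative approach as it would tend toward smaller treatment effect". Under SAP 9.8.1.3, BOCF applies to the primary endpoint only when a subject has no diary data after randomization. Everyone else is averaged over the days recorded; Protocol 9.10.1 sets the minimum: "For subjects with at least one day of cataplexy attack data".

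**The concern.** The protocol leaves the description of these analyses to the SAP; it does not say that they may be omitted. The SAP makes both missing-data analyses conditional and does not disclose it where changes are listed. The condition pools the arms, so a loss concentrated in one arm can stay below it. ESS appears to inherit a trigger defined on cataplexy diaries.

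The primary estimate rests on whatever days were recorded. In a withdrawal design, a JZP-258 subject who stops after Week 1 keeps a score earned on drug, whereas the control-based MI assumes that such subjects drift toward placebo. The MI is the only planned re-estimate under that less favourable assumption, and it is the one that may not be run.

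The conservatism statement has a related flaw. Zero change shrinks the treatment difference when given to a placebo dropout, but is favourable when given to a JZP-258 dropout. The SAP makes the opposite assumption for JZP-258 dropouts when it introduces the control-based MI.

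**Working it through.** **Inputs.** Protocol 9.3: 65 per arm, difference 17.5 attacks/week, SD 30, two-sided 0.05, t-test. SAP 9.8.1.5: trigger above 5% of the EFF. Assumptions: EFF = 130; JZP-258 mean change 0 in each week; placebo rises w1 and w2 in Weeks 1 and 2 averaging 17.5, so w1 = 35 − w2. The documents give no dropout rate for the double-blind period.

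**1. The plan's own figure.** SE = 30 × √(2/65) = 5.26. Power is 0.910 (noncentral t, 128 df) or 0.914 (normal). The stated 90% or more reproduces.

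**2. The threshold.** 0.05 × 130 = 6.5, so the analyses run from 7 subjects upward. Six subjects are 6/130 = 4.6% overall and 6/65 = 9.2% of one arm. For an EFF of 120 or 140, the most that can go unexamined is 6 or 7.

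**3. Who is scored how.** SAP 5.5 requires at least one of each efficacy assessment after randomization, cataplexy included, for entry to the EFF. Read literally, that removes the only subjects who would receive primary BOCF under SAP 9.8.1.3. A subject with a missing week who remains in the EFF is scored by the available-day average.

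**4. Available-day average against control-based imputation, JZP-258 arm.** A subject who stops after Week 1 scores 0 by the first method and (0 + w2)/2 by the second. With k such subjects the effect is overstated by (k/65) × (w2/2). For k = 6:

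| Placebo Week 2 rise (w2) | Overstatement, attacks/week | In SE | Power at the reduced effect |
|---|---|---|---|
| 17.5 | 6/65 × 8.75 = 0.81 | 0.15 | 0.883 |
| 25 | 6/65 × 12.5 = 1.15 | 0.22 | 0.869 |
| 35 | 6/65 × 17.5 = 1.62 | 0.31 | 0.850 |

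Against the planned 17.5, these run from 4.6% to 9.2%.

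**5. Offset from the placebo arm.** A placebo subject who stops after Week 1 scores w1 instead of 17.5, which understates the effect by 17.5 − w1 = w2 − 17.5. Net overstatement = [kJ × w2/2 − kP × (w2 − 17.5)]/65, where kJ and kP are the numbers lost in the JZP-258 and placebo arms.

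- Three per arm: 0.40 at w2 = 17.5; (37.5 − 22.5)/65 = 0.23 at 25; 0 at 35.
- Six placebo, none JZP-258: 0 at 17.5; −6 × 7.5/65 = −0.69 at 25; −1.62 at 35.

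**6. Direction of BOCF, wherever it did apply.** With imputed shares dJ and dP, BOCF gives 17.5 × (1 − dP) and control-based imputation 17.5 × (1 − dJ). The gap is 17.5 × (dJ − dP): +1.62 for a 6/0 split (JZP-258/placebo), 0 for 3/3, −1.62 for 0/6. BOCF is conservative only when placebo loses the larger share.

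**The case against.** The best defence is that the protocol hands the specification to the SAP, and a prespecified trigger that ignores treatment arm is arguably within that delegation. The SAP also gives a reason: the design is enriched, and discontinuation was rare in a similar study. This makes the omission from SAP 3.6 partly a disclosure matter. It does not justify the condition: if discontinuation is rare, always running the MI costs almost nothing.

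Four stronger readings are tempting and are not supported.

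- A reader might infer that BOCF biases the primary result toward the drug. The EFF rule appears to leave no subject for primary BOCF, so 1.6 cannot be presented as a BOCF effect.
- A reader might infer that the threshold is justified by the conservatism claim. The SAP ties it to rarity; the conservatism sentence is a separate error.
- A reader might infer that the trigger will rarely fire. Without a double-blind dropout rate this cannot be said: at N = 130, the chance of 7 or more is 0.10 if each subject has a 3% chance of a missing week, 0.48 at 5% and 0.81 at 7%.
- A reader might infer that nothing planned would reveal differential dropout. SAP 9.1 tabulates withdrawals by randomized arm, and the per-protocol analysis is not subject to the 5% condition. Neither re-estimates the effect under a different missing-data assumption.

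All six losses falling in the JZP-258 arm is also extreme: (1/2)^6 = 1.6% if each is equally likely to be in either arm.

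**Conclusion.** The point holds, at modest size. An unconditional protocol commitment has become conditional in the SAP without being listed, and the conservatism statement is wrong without an arm qualifier. With 130 subjects, up to 6 can lack a week unexamined. The largest overstatement below the threshold is about 0.8 attacks/week if placebo worsening is flat across the two weeks, and 1.6 if it all falls in Week 2. Protocol 3.1.3 describes a gradual increase over both weeks in the earlier Xyrem withdrawal study, so an intermediate value is reasonable. Balanced loss leaves 0 to 0.4; loss confined to placebo removes the overstatement or reverses it.

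These figures assume an EFF of 130, no change on JZP-258, and imputation at the placebo Week 2 mean. The SAP's model also conditions on the Week 1 value, so a subject still near baseline in Week 1 would probably be imputed lower and the shift would be smaller. The figures are on the mean scale and do not carry over directly to the rank analysis used if normality is rejected. A shift of at most 0.31 SE would matter only for a borderline result.

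**What to change.** In SAP 9.8.1.5, delete the 5% condition so that the control-based MI is always run for the primary endpoint. It is already specified, seeds included; only its pointer to section 9.8.4 for the primary analysis needs correcting to 9.8.1.4. Replace the conservatism sentence with one saying that zero change shrinks the effect for placebo dropouts and favours the drug for JZP-258 dropouts. Reconcile SAP 9.8.1.3 with SAP 5.5, so that it is clear whether any subject in the EFF can receive BOCF. If any condition is kept, list it in SAP 3.6.

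The ESS sensitivity analysis should also run without the threshold. Its imputation model still has to be written, because the cataplexy model uses two weekly values and ESS has one assessment after randomization.

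Label: wrong as written. The cost is SAP wording, one short ESS specification and a little extra analysis work; the primary analysis does not change.

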#### ***Multiple Imputations – Control-Based Imputation***

Average weekly number of cataplexy attacks will be computed for each week of the DB RWP separately based on the available data during each respective week (Week 1 and 2). If no data are available for a given week, a multiple imputation approach will be used to impute the average number of cataplexy attacks for that week based on an imputation model that will account for available data from the imputed subject as well as other similar subjects in the study. Multiple imputation approach, as described in detail below, will reasonably account for uncertainty of incomplete data and implement clinically reasonable assumptions regarding outcomes that could be observed while the subject is on or off study treatment during the weeks when missing data occur.

The control-based imputation method uses the data from the subjects in the placebo treatment group to impute the missing values for the subjects in the JZP-258 treatment group. This assumes that subjects who withdraw from the JZP-258 treatment group will have their efficacy tend toward that of the subjects in the placebo treatment group after treatment discontinuation. The missing data assumptions for each treatment group are as follows:

- Placebo: Missing data for subjects from the placebo treatment group, both non-monotone (intermittent) and monotone (data completely missing from a given time point through the end of the DB RWP), will be imputed under the assumption of the missing at random (MAR) mechanism, where these subjects are assumed to have unobserved values in line with similar placebo subjects with available data, taking into account their values observed prior to time points with missing data (i.e., baseline week cataplexy and/or cataplexy in week 1, as appropriate). This imputation approach accounts for the trial effect while no active treatment is taken.
- JZP-258: For subjects from the JZP-258 treatment group, non-monotone missing data will be also imputed under the MAR assumption. This is justified as subjects will remain on randomized treatment while intermittent missing data may occur and thus may be modeled based on similar subjects from their randomized treatment group. Monotone missing data will be imputed under the missing not at random (MNAR) assumption from the same MAR-based imputation model estimated from the placebo subjects, assuming that the JZP-258 subjects with missing data will drift towards the average weekly number of cataplexy attacks during the DB RWP of the placebo treatment group, reflecting the outcomes that would be observed when active randomized treatment is no longer taken. The MNAR imputation will be achieved by estimating the imputation model for the JZP-258 treatment group using available data only from the placebo treatment arm. (O'Kelly and Ratitch 2014).

This control-based multiple imputation will be performed through 2 steps.

1. First, non-monotone missing average weekly number of cataplexy attacks (i.e., the average weekly number of cataplexy attacks is missing for Week 1, but not for Week 2; usually relatively infrequent) will be imputed under the MAR assumption using a multivariate joint Gaussian imputation model and the Markov Chain Monte Carlo (MCMC) method. A separate imputation model will be estimated within each treatment group. The imputation models will include the average weekly number of cataplexy attacks computed over the whole OL SDP as covariate, the Pre-Randomization Group and the average weekly number of cataplexy attacks for each week during the DB RWP (i.e., Week 1 and Week 2). The MCMC method of the SAS v9.4 MI procedure will be used with a random seed number of 141016, multiple chains, 200 burn-in iterations, and a non-informative (Jeffrey's) prior.

During this step, a 100 imputed datasets will be created.

2. Once all the non-monotone missing data have been imputed, the monotone missing average weekly number of cataplexy attacks for each week during the DB RWP will be imputed using a predictive mean matching method (Heitjan F and Little RJA, 1991; Schenker N and Taylor JMG, 1996) for each imputed dataset. To impute Week 1, only the placebo subjects with non-missing weekly average for Week 1 will be used for the estimation of the imputation model, while JZP-258 subjects with non-missing weekly average for Week 1 will be excluded from the estimation of this imputation model. The multiple imputation regression model for imputation of values at Week 1 will include explanatory variables for the average weekly number of cataplexy attacks computed over the whole OL Stable-Dose Period, the Pre-Randomization Group and stimulant use in the OL Stable-Dose Period as a binary variable. Similarly, to impute Week 2, only the placebo subjects with non-missing weekly average for Week 2 will be used for the estimation of the imputation model, while JZP-258 subjects with non-missing data at Week 2 will be excluded from the estimation of this imputation model. The multiple imputation regression model for imputation of values at Week 2 will include the same covariate and factors as the model for Week 1 as well as the average weekly number of cataplexy attacks for Week 1 of the DB Randomized-Withdrawal Period. This step will be implemented using the SAS v9.4 MI procedure and the MNAR statement with MODELOBS option to specify that only observations from the placebo group should be used for estimation of the imputation model. The random seed number for the predictive mean matching multiple imputation will be 160520 and the number of close predicted values used in the selection of each imputed value will be SAS default value (i.e.,  $k = 5$ ).

Average weekly number of cataplexy attacks during the whole DB RWP will then be computed from the multiply imputed weekly data as (average weekly number of cataplexy attacks for Week 1 + average weekly number of cataplexy attacks for Week 2) / 2. Multiply imputed datasets will be analyzed using the same methods as in the primary analysis (see [section 9.8.4](#)), either as continuous or rank data. Results from analysis of each imputed dataset, i.e., LS mean treatment differences and their SEs, will be combined using Rubin's combination rule (1987), as implemented in SAS MIANALYZE procedure, to produce a pooled LS mean treatment difference and its 95% CI. The pooled p-value for the test of null hypothesis of no treatment effect will be provided.

Although the MCMC method for non-monotone missing data assumes multivariate normality, inferences based on multiple imputation can be robust to departures from multivariate normality if the amount of missing data is not large, because the imputation model is effectively applied not to the entire dataset but only to its non-monotone missing data (Schafer JL 1997). Furthermore, for monotone missing data, the predictive mean matching method ensures that imputed values are plausible and might be more appropriate than the regression method if the normality assumption is violated (Horton NJ and Lipsitz SR, 2001).

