### **3.4. SAMPLE SIZE JUSTIFICATION**

Up to 185 subjects will be enrolled in the study to ensure a minimum of 130 subjects (65 subjects per treatment group) enter the DB RWP. This includes at least 50 subjects on Xyrem and 60 subjects using Xyrem plus other antiepileptics or non-Xyrem antiepileptic alone, as applicable.

A sample size of 65 subjects randomized per treatment group will provide at least 90% power to detect a difference in the change in mean weekly cataplexy attacks, from the OL SDP to the DB RWP, of 17.5 between JZP-258 and placebo. This assumes a common standard deviation (SD) of 30 and a two-sided significance level of 0.05 using a t-test. Assuming a 30% dropout rate prior to randomization, approximately 185 subjects will be enrolled to ensure that a minimum of 130 subjects enter the DB RWP. Assumptions were conservatively based on previous completed Xyrem studies GHB-2, OMC-SXB-15, and OMC-SXB-21 and account for study design. From these 3 studies, the mean weekly reduction in cataplexy attacks of Xyrem compared to placebo (common SD) ranged from approximately 10 (30) to 16 (28).

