## 9.8.1. PRIMARY EFFICACY ENDPOINT

### 9.8.1.1. PRIMARY EFFICACY ENDPOINT & DERIVATION

The primary efficacy endpoint is the change in average weekly number of cataplexy attacks from the two weeks of the OL SDP to the two weeks of the DB RWP.

Subjects will complete a daily cataplexy frequency diary each night prior to bedtime to record the number of cataplexy attacks that they had that day beginning at Study Day 1 up to the end of the DB RWP visit. Daily cataplexy frequency diary will not be collected during OLE.

For subjects with at least one day of cataplexy attack data, the average weekly number of cataplexy attacks over each of the two weeks (see Table 1) of the OL SDP will be calculated as follows:

$$\frac{\text{Total number of cataplexy attacks within the OL SDP period}}{\text{Number of days with non-missing data within the OL SDP period}} \times 7 \text{ days}$$

Average weekly number of cataplexy attacks over each of the two weeks of the DB RWP will be calculated similarly. Additionally, average weekly number of cataplexy attacks by week for each study period (see Table 1) will also be calculated as follows:

$$\frac{\text{Total number of cataplexy attacks within a week}}{\text{Number of days with non-missing data within that week}} \times 7 \text{ days}$$

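### The control-based imputation fills only double-blind weeks with no diary entry at all, so days lost within a partly recorded week never come under the placebo-based assumption

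*SAP*

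**What the plan says.** - **Primary derivation.** Protocol 9.10.1 and SAP 9.8.1.1 divide all attacks by all recorded days in the two-week period and multiply by 7, for anyone with at least one recorded day. For the double-blind period SAP 9.8.1.1 states: "Average weekly number of cataplexy attacks over each of the two weeks of the DB RWP will be calculated similarly". The by-week value uses the same ratio within one week. Neither has a minimum number of double-blind days; the 10-of-14-day diary rule in Protocol 6.12.7 applies to the Stable-Dose Period.
- **Windows.** SAP Table 1 sets double-blind Week 1 as Period Days 2 to 8 and Week 2 as Day 9 to the date of Visit 16. Protocol Appendix 1.1 allows that visit up to 3 days late.
- **Purpose.** SAP 9.8.1.5 says that, to check the averaging of diary values "regardless of the number of non-missing values available over the two-week DB RWP, sensitivity analyses will be performed".
- **Control-based imputation.** Weekly values come from the available days, and "If no data are available for a given week, a multiple imputation approach will be used". JZP-258 subjects with monotone missing weeks are imputed from placebo data, on the premise that they drift towards placebo after stopping drug. Both imputation steps act only on missing weekly averages.
- **Combination.** The two-week value is then "average weekly number of cataplexy attacks for Week 1 + average weekly number of cataplexy attacks for Week 2) / 2", the simple mean of the two weeks. No other rule is given for subjects with nothing imputed.
- **LOCF.** The second planned analysis works by day and replaces each missing day with the last recorded daily count.
- **Trigger.** Both analyses run only if more than 5% of the Efficacy Population lack Week 1 or Week 2 data.

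**The concern.** The control-based analysis is meant to ask what happens if JZP-258 subjects who stop behave like placebo subjects afterwards. As written, it asks this only of subjects who lose a whole week. A JZP-258 subject who stops early in Week 2 keeps a Week 2 value that is one or two on-drug days scaled to a week, and is not moved towards placebo. A subject who stops early in Week 1 has Week 1 fixed from a few days, and that figure is then a predictor when Week 2 is imputed. The analysis thus tests only in part the reliance on few diary days that it was set up to examine.

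The simple mean of the two weeks adds a second change. For some subjects the endpoint value moves although nothing was imputed, so a difference from the primary result would not be due to the missing-data assumption alone.

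**Working it through.** **The plan's own figure, for scale.** SAP 3.4 states: "A sample size of 65 subjects randomized per treatment group will provide at least 90% power", for a difference "of 17.5 between JZP-258 and placebo", a "common standard deviation (SD) of 30" and "a two-sided significance level of 0.05 using a t-test". The standardized difference is 17.5 / (30 × √(2/65)) = 3.33, which gives power 0.914 by the normal approximation and 0.910 by the noncentral t with 128 df. Enrolment is 130 / 0.70 = 185.7, against 185 stated. Both reproduce and neither is disputed; 17.5 serves below as a yardstick.

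**Which lost days escape imputation.** Take the nominal window, Period Days 2 to 15. Assume that the diary ends for good on Day d, with d equally likely from 2 to 14.
- Days lost: the sum of (15 − d) = 91.
- For d = 2 to 8 (7 cases), Week 2 is empty, so 7 days are imputed each time: 49. The days lost in Week 1 (6+5+4+3+2+1+0 = 21) are not.
- For d = 9 to 14 (6 of 13 cases), nothing is imputed: 6+5+4+3+2+1 = 21 days.
- Never imputed: 21 + 21 = 42 of 91 (46%).

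**One subject.** Assume a JZP-258 subject with 1 attack/day on drug and 4/day off drug (placebo-like). With a last entries, the day-level value is 7 × [a × 1 + (14 − a) × 4] / 14.

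| Diary entries (last Period Day) | Primary | LOCF | Planned control-based | Control-based by day |
|---|---|---|---|---|
| 7 (Day 8) | 7.0 | 7.0 | 7 × (1+4)/2 = 17.5 | 17.5 |
| 8 (Day 9) | 7.0 | 7.0 | 7 × (1+1)/2 = 7.0 | 16.0 |
| 10 (Day 11) | 7.0 | 7.0 | 7.0 | 13.0 |

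One extra entry takes the planned value from 17.5 to 7.0. A diary that simply ends leaves at most six days un-imputed, so at these rates the largest gap is 7 × 6 × (4 − 1) / 14 = 9.0 attacks/week.

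**Simple mean against pooling, nothing imputed.** Assume 2 attacks/day in Week 1 and 4/day in Week 2. Pooled = 7 × (2 × d1 + 4 × d2) / (d1 + d2), where d1 and d2 are the diary days; simple mean = 7 × (2 + 4)/2 = 21.0.

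| Days in Week 1 + Week 2 | Pooled (primary) | Simple mean |
|---|---|---|
| 7 + 7 | 21.00 | 21.0 |
| 7 + 5 | 19.83 | 21.0 |
| 7 + 2 | 17.11 | 21.0 |
| 7 + 1 | 15.75 | 21.0 |
| 1 + 7 | 26.25 | 21.0 |
| 7 + 10 (complete diary, Visit 16 three days late) | 22.24 | 21.0 |

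The values differ only if both the day counts and the daily rates differ between weeks. With independent days at a constant rate, the within-subject variance ratio of simple mean to pooled is [(1/7 + 1)/4] / (1/8) = 2.29 with one Week 2 day and [(1/7 + 1/2)/4] / (1/9) = 1.45 with two.

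**Effect on the arm mean.** Assume that 1 to 7 of 65 JZP-258 subjects have the largest gap. The shift is 9.0 × 1/65 = 0.14 to 9.0 × 7/65 = 0.97 attacks/week, or 0.8% to 5.5% of 17.5.

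**Effect of a 4-day minimum.** In the same dropout model, the days still not imputed are 3+2+1 in Week 1 (d = 5 to 7) and 3+2+1 in Week 2 (d = 12 to 14): 12 of 91 instead of 42.

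**The case against.** - **LOCF fills single days.** The SAP assigns the robustness aim to its sensitivity analyses together, not to the control-based one alone. A reader might infer that no planned analysis touches days lost within a week; the LOCF paragraph rules that out. What remains is that LOCF holds a JZP-258 subject at the last recorded count, so no control-based analysis covers partial weeks.
- **Equal weighting is defensible.** With different rates in the two weeks, the simple mean returns the complete 14-day value (21.0) in every 14-day pattern above, while pooling gives 15.75 or 26.25. This stands. The simple mean is not an error; it is noisier when a week has few days, and it changes a second thing along with the missing-data assumption.
- **The effect may be negligible.** The SAP expects few double-blind discontinuations, citing a similar Xyrem study. Protocol 3.1.3 calls the rise in the earlier withdrawal study small as well as gradual. A rank-based analysis, if the normality test leads to it, would limit single values further. This stands and bounds the point.
- **A cut-off is arbitrary and discards counts.** The figure of 4 is a judgement. The loss of counts is avoided if observed days are kept. A subject still on drug who merely stops the diary would be imputed as placebo, but the plan already does that when Week 2 is empty.

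**Conclusion.** The point holds in limited form, as a cheap improvement. The control-based analysis does not apply its own assumption to days lost within a partly recorded week, and it tests reliance on few diary days only in part. The two-week value departs from the primary one in some patterns with nothing imputed.

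Stronger readings are not supported. A reader might infer that every subject without imputed data gets a different value; with 7 + 7 days the values are identical. A reader might take 46% as a forecast; it rests on an assumed uniform dropout day, and the documents do not say how many partial weeks to expect. Nor is the main result in doubt: the primary test, alpha and sample size are untouched, and the analysis runs only above the 5% trigger. If that trigger is read by whole weeks, partial weeks would not count towards it either.

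The effect is probably small: under the assumed rates and 1 to 7 affected subjects, at most about 1 attack/week on the arm mean, against a planned difference of 17.5.

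**What to change.** In SAP 9.8.1.5, prespecify a minimum number of diary days, for example 4 of 7, below which a double-blind week is treated as missing in the imputation models, control-based for JZP-258 when monotone.

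Preferably keep the observed days and apply the imputed rate only to the missing ones: two-week value = 7 × [recorded attacks + (imputed weekly value / 7) × missing days in that week] / days in the window. No recorded counts are then discarded, and a subject with no missing days keeps the primary pooled value, including when Visit 16 is late. State also how the few lost days in a week that meets the minimum are handled, for example at that week's own recorded mean.

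The cost is a judgement on the cut-off, a short paragraph of SAP text and a few lines of code. Days lost in weeks that meet the minimum still escape the control-based assumption. The primary analysis does not change.
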